#### 8.4.2 Study-Level Stopping Criteria

Following assessment by the Data Safety Monitoring Board (DSMB, see [Section 10.9](#)), the study is to be stopped as shown below:

- If  $\geq 4$  subjects on the brequinar treatment arm develop the same Grade 3 or 4 adverse event or symptomatic laboratory abnormality
- If  $\geq 8$  subjects on the brequinar treatment arm develop any Grade 3 or 4 adverse event or symptomatic laboratory abnormality.

### 8.5 Hospital Discharge Prior to Study Day 15

Subjects discharged from the hospital prior to the Day 15 visit are to return to a research facility when feasible for the remaining study visits. All scheduled study assessments are to be completed at these visits when conducted at a research facility.

PROTOCOL NUMBER: CCB-CRISIS-01  
PROTOCOL VERSION FINAL DATE: 10SEPT2020

Page 30 of 58

For subjects in the brequinar treatment group discharged from the hospital prior to Day 5, the subject is to take home the remaining doses of brequinar for daily self-administration. All subjects (brequinar and SOC) should have the scheduled assessments, e.g. lab samples and the nasopharyngeal swab, on the day of discharge and enter these results on the appropriate EDC page. Following discharge, subjects are to return to the research or out-patient lab collection facility for the remaining study visits, if feasible. Out-patient lab results are to be entered into the EDC and reviewed by a member of the study team. It is important that every effort be made to have subjects return at least on Days 7 and 15, if feasible. Subjects in the brequinar group are to record brequinar dosing on the medication diary provided by the study team. The study team will arrange for the subject to return any unused study medication to the research facility.

For all subjects, if discharge occurs on Days 10, 11, or 12, ensure a hematology/chemistry sample has been obtained on the day of discharge and record these results on the appropriate EDC page. Following discharge, the subject is to return to the research or out-patient lab collection facility for the Day 15 visit, if feasible. Out-patient lab results are to be entered into the EDC and reviewed by a member of the study team.

If discharge occurs on Days 13, 14 or 15, complete the Day 15 Final Visit activities prior to discharge. No further visits are required unless follow up is needed for a study drug-related AE or an SAE; the Day 29 mortality assessment is still to take place.

If the subject is unable or not permitted to return for planned study visits, the visit activities will be conducted by contacting the subject (phone or other digital media) except for the lab draw. The lab draw will be completed at a research facility or an outpatient laboratory, if feasible, and the results entered into the EDC and reviewed by the study team.

Study completion or the reason for study discontinuation will be recorded in the source document and the eCRF. A subject is considered completed the study if they have assessments through Day 15, whether conducted in the hospital or contacted via phone or other digital media.

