Investigational Product and Dosage	
Subjects will be randomized in a 1:2 ratio to either standard of care (SOC) alone, or SOC + brequinar.
 
Brequinar is available as 100 mg oral capsules. Five once daily doses of brequinar 100 mg are to be administered on Study Days 1 – 5 for those assigned to the SOC + brequinar group.

	Treatment assignment will be randomized, open label.
Primary Objective	
 
To determine the safety and tolerability of SOC and SOC plus brequinar in hospitalized COVID-19 subjects.
 

Secondary Objectives	
 
To determine the rates of/changes in clinical status measures listed through Day 15:                             
 
Hospitalization status
 
Duration of hospitalization
 
NEWS2 Score
 
 
 
Mortality through Day 29
 

Exploratory Objectives	
 
To determine the change in SARS-CoV-2 nasopharyngeal viral load through Day 15
 
To determine the change in inflammatory markers through Day 15
 
To determine the change in DHO levels through Day 15
 
To determine the change in brequinar concentration levels through Day 7
 

Design	
This will be a phase 1a randomized, open label, multi-center study with approximately 24 subjects. All subjects will receive SOC per institutional guidelines for treatment of patients with COVID-19 infection. In addition to SOC, the brequinar group will receive brequinar 100 mg once daily for 5 days.
 
Subjects will have a Screening Visit followed as soon as possible with Study Day 1 (Day 1 may take place on the same day if entry criteria data are available). Study procedures are presented in detail in the procedures section, see below. Subjects will be followed through Day 15. Mortality will be assessed at Day 29.
 
See below for instructions regarding hospital discharge prior to Day 15.
 
Hematology and chemistry results and study information such as NEWS2 criteria are to be collected using the available EHR data as much as possible to avoid extra procedures for the study.

Sample Size:	Approximately 24 subjects will be randomized to either standard of care or standard of care plus brequinar in a 1:2 ratio (approximately 8 assigned to standard of care and 16 subjects on brequinar).
Number of Sites:	1 - 8
Study Period:	An enrollment period of 3 months is expected.

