	
 
• Participants who develop a Grade 4 symptomatic toxicity, regardless of relatedness to study drug, are to be permanently discontinued from study treatment.
 
• Subjects who develop Grade 3 or 4 toxicities are to be followed by re-evaluation every 2 days, as feasible, until the toxicity returns to <math>\leq</math> Grade 2 severity.
 
 
Study-Level Stopping Criteria:
 
The study is to be stopped as shown below:
 
 
• If <math>\geq 4</math> subjects on the brequinar treatment arm develop the same Grade 3 or 4 adverse event or symptomatic laboratory abnormality
 
• If <math>\geq 8</math> subjects on the brequinar treatment arm develop any Grade 3 or 4 adverse event or symptomatic laboratory abnormality.
 

DSMB
	
A Data Safety Monitoring Board (DSMB) will meet periodically to review the safety and scientific conduct of the study. At a minimum, the DSMB is to review adverse events and safety laboratory assessments after the first six subjects complete Day 5 of treatment, and again after the first 12 subjects complete Day 5 of treatment.

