## Treatment

The treatment period is up to 5 days: standard of care alone (SOC) or SOC + brequinar 100 mg daily for 5 days. Data points such as NEWS2 Assessments are to be collected from the EHR when possible, a separate visit by study staff is not to be conducted. The first dose of brequinar is to be given as soon as possible depending on availability of investigational pharmacy staff. If the subject is discharged from the hospital prior to Day 15, see [Section 8.5](#) for how and when to conduct study assessments.

It is understood that some assessments may not be conducted if the subject is unable to return to the clinic after discharge due to restricted travel or if the study visit cannot be conducted remotely; this will not be counted as a protocol deviation. Collect information from the EHR, medication records and Progress Notes whenever possible

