### **10.8 Safety Monitoring for Hematologic Toxicities**

Myelosuppression is a known effect of DHODH inhibition that is associated with prolonged exposure and high doses. To reduce the risk of this effect with brequinar in COVID-19 subjects, the extensive brequinar safety database with over 1,000 patients has been evaluated to select a dose level expected to be safe and well tolerated with regard to hematologic toxicity. In addition to enhancing safety by selecting a relatively brief 5-day exposure and a low brequinar dose, all subjects in the clinical trial will initially be hospitalized as in-patients and will be under the care of highly qualified infectious disease, critical care, and associated medical personnel. As is standard of care for moderately to severely ill in-patients, daily samples will be obtained for hematology assessments including complete blood count with full differential (WBC, RBC, hemoglobin, hematocrit, platelet count, absolute neutrophils, absolute lymphocytes, absolute monocytes, absolute eosinophils, and absolute basophils). Any clinically significant out-of-range laboratory values will be assessed by hospital staff in a timely manner and treatment needs addressed as appropriate. Clinically significant out-of-range laboratory results will be reported as adverse events.

In addition to real time assessments by the treating clinical team, the Clear Creek Medical Monitor will assess the available hematology data on a weekly basis to identify any pathologic trends or safety issues. Any apparent increase in the expected rate or severity of hematologic safety events will be discussed with the Principal Investigators, the Sponsor, and the Medical Monitor. In addition, the Data Safety Monitoring Board will assess available hematology data on a periodic basis to independently assess any pathologic trends or safety issues. If the rate or severity of hematologic toxicities appears to be above the expected rate or the severity appears worse than that expected, the trial enrollment will be suspended and no further subjects will be treated while a comprehensive data review is conducted. Depending on the outcome of the safety review the study may be stopped, the design adjusted, or the study may continue as designed. Individual and study stopping rules are provided in [Section 8.4](#).

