### **10.9 Data Safety Monitoring Board**

A Data and Safety Monitoring Board (DSMB) will be established to provide independent oversight to this trial. The primary responsibility of the DSMB will be to review the progress and conduct of the trial in order to maintain scientific rigor and to ensure the wellbeing of subjects participating in the trial. The specific responsibilities of the DSMB will be detailed in a separate DSMB charter. The DSMB will include at a minimum at least one statistician and two clinicians who will perform periodic data review to assess whether there are clinically significant differences between treatment arms that could affect participant safety. Following such a review, the DSMB Chair will advise the Sponsor that the study be stopped, the design changed, or that the study may continue per protocol.

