#### **10.9.1 DSMB Safety Review Schedule**

The DSMB is to review adverse events and safety laboratory assessments after the first six subjects complete Day 5 of treatment, and again after the first 12 subjects complete Day 5 of treatment.

PROTOCOL NUMBER: CCB-CRISIS-01  
PROTOCOL VERSION FINAL DATE: 10SEPT2020

Page 46 of 58

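### The stopping count of eight severe-event subjects will mostly be crossed after the last fixed DSMB review, and reaching it convenes no meeting

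*Protocol*

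**What the plan says.** All references are to the protocol version dated 10 September 2020.

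- **Rule.** Section 8.4.2 has two study-level criteria: at least 4 brequinar subjects with the same Grade 3 or 4 event, or at least 8 "subjects on the brequinar treatment arm develop any Grade 3 or 4 adverse event or symptomatic laboratory abnormality". It applies them following assessment by the DSMB. The synopsis (Stopping Criteria) gives the same two criteria and says the study is to be stopped, with no mention of prior DSMB assessment.
- **Fixed reviews.** Section 10.9.1 sets one review after the first six subjects and one "again after the first 12 subjects complete Day 5 of treatment". Neither names an arm.
- **Other meetings.** The synopsis has the DSMB meeting periodically and treats the two reviews as a floor: "At a minimum, the DSMB is to review adverse events and safety laboratory assessments" at those points. No later review is dated.
- **Arm sizes and accrual.** The synopsis plans "approximately 8 assigned to standard of care and 16 subjects on brequinar", and "An enrollment period of 3 months is expected".
- **Who has a treatment period.** Section 9.5 defines it for both arms: "The treatment period is up to 5 days: standard of care alone (SOC) or SOC + brequinar 100 mg daily for 5 days".
- **Other routes.** If hematologic toxicity looks worse than expected, Section 10.8 says "the trial enrollment will be suspended and no further subjects will be treated while a comprehensive data review is conducted". Under Section 10.9, after a review "the DSMB Chair will advise the Sponsor that the study be stopped, the design changed, or that the study may continue per protocol".

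**The concern.** The criterion of 8 with any severe event is the only study-level count that picks up a mixture of different severe events. The criterion of 4 with the same event does not, and Section 10.8 covers hematologic toxicity only. Yet the protocol fixes its reviews at points where about 4 and then about 8 brequinar subjects have finished treatment, so the count can hardly be met there. It comes into play in the second half of enrolment. There the protocol schedules nothing and does not say that reaching the count convenes the DSMB or holds new dosing. A site and sponsor following the text as written could cross the count and go on randomising and starting subjects until an undated meeting.

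**Working it through.** **Inputs.** 24 subjects at 1:2, thresholds 4 and 8, and reviews at 6 and 12 subjects are from the protocol. The all-cause Grade 3/4 rate p in hospitalised COVID-19 patients is not given, so 30 to 70% is assumed. The one documented figure, 2 of 39 (5.1%, Section 8.2.1), is drug-related and from oncology studies, and is not a background rate for this population.

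**The plan's own figure.** 24 × 2/3 = 16 brequinar, which reproduces. By the same ratio, 6 × 2/3 = 4 and 12 × 2/3 = 8 brequinar completers at the two reviews.

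**First review.** At most 6 subjects have completed Day 5, so 8 events among completers are impossible.

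**Second review.** P(X ≥ 8) with X ~ Bin(n, p). With n = 8 this is p⁸; for example 0.5⁸ = 0.0039. Further brequinar subjects may be on treatment by then: 24 in 13 weeks is 1.85 per week, and 1.85 × 2/3 × 5/7 week = 0.88. So n = 9 and n = 10 are shown too.

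| Quantity | p = 30% | 40% | 50% | 60% | 70% |
|---|---|---|---|---|---|
| Count met at second review, n = 8 | <0.01% | 0.07% | 0.4% | 1.7% | 5.8% |
| n = 9 | 0.04% | 0.4% | 2.0% | 7.1% | 20% |
| n = 10 | 0.2% | 1.2% | 5.5% | 17% | 38% |
| Count met by n = 16 | 7% | 28% | 60% | 86% | 97% |

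Averaged over random splits of the first 12 (12 drawn from a fixed 16:8, or simple 1:2), the second-review probability is 1.2 to 1.9% at 50%, 4.0 to 5.7% at 60% and 10.5 to 13.6% at 70%.

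**Share of crossings after the last fixed review.** 1 − P(X ≥ 8 | n) / P(X ≥ 8 | 16). At 50% with n = 8: 1 − 0.0039/0.5982 = 0.993. For 50/60/70% the shares are 99/98/94% (n = 8), 97/92/80% (n = 9) and 91/80/61% (n = 10).

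**Subjects exposed after a crossing.** Let T be the brequinar subject in whom the eighth event occurs. Given T ≤ 16, and one further subject started before the event is known, the number still to be treated is E[max(16 − T − 1, 0)]: 0.9/1.2/1.8/2.6/3.8 at 30/40/50/60/70%. With no lag at all it would be 2.6/3.6/4.7 at 50/60/70%.

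**If 10.9.1 meant brequinar subjects only.** The second review would fall at n = 12, where the count is met in 0.9/5.7/19/44/72% at 30 to 70%. How the rule behaves thus depends on an arm that the section does not name.

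**The case against.** The strongest reply is that the rule was never confined to the two reviews. The synopsis states it without the DSMB condition, and the wording in 8.4.2 can be read as the DSMB assessing once the count is reached. Both versions are cumulative, and a threshold of half the arm is not faulty merely because it cannot be met at half accrual. This stands to a point: a reader might infer that the criterion can never act, and the documents do not support that. But the two statements differ, and neither says that reaching the count calls a meeting or holds dosing.

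A reader might also infer that the DSMB is powerless at the second review. It is not. Section 10.9 lets it advise stopping or changing the design without any count. At true rates of 50/60/70% it would see at least 5 of 8 brequinar subjects with severe events in 36/59/81% of trials. The criterion of 4 with the same event is also workable there (4 of 8).

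Finally, severe events in the second half would not go unseen. SAEs are reported within 24 hours (10.5), adverse events are reviewed daily until discharge (9.5), individual discontinuation rules apply (8.4.1), hematologic toxicity suspends enrolment (10.8), and the sponsor or an investigator may end the study (9.8). The DSMB charter is not shown and may provide for ad hoc meetings. All of this reduces the harm. None of it ties the count of 8 to an action, and the 10.8 suspension is limited to hematology.

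**Conclusion.** The point holds as a mismatch between the stopping rule and the review schedule, with modest consequences. The count of 8 is essentially out of reach among completers at both fixed reviews, unless the true severe-event rate is very high or subjects still on treatment are counted. Most crossings (61 to 99% at rates of 50 to 70%, with 8 to 10 subjects counted) come after the last dated review. Given a crossing and a one-subject reporting lag, about 1 to 4 brequinar subjects would still be treated. At low event rates the count is seldom reached at all (7% at a rate of 30%).

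This rests on counting both arms towards the 6 and 12, which is the natural reading because the treatment period is defined for both, and on assumed event rates. It does not show that the numbers 4 and 8 are wrong, or that safety oversight is absent in the second half of the trial. It is a cheap improvement to a safety provision whose protocol wording is incomplete and differs between the synopsis and Section 8.4.2.

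**What to change.** Keep 4 and 8. State the following identically in 8.4.2, 10.9.1 and the synopsis:

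> When either count is first reached in the brequinar arm, no further subject is randomised or given a first dose, and an unscheduled DSMB review is held at once. The study stops unless the DSMB, having compared events with the concurrent SOC arm, documents why it may continue.

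In 10.9.1, define the scheduled reviews as after 4 and 8 brequinar-treated subjects complete Day 5. This keeps roughly the present timing and matches the arm that the rule counts. A third review at 12 brequinar-treated subjects is a useful but secondary backstop: it would find the count met in only 19/44/72% at 50/60/70%, so the trigger does the main work. Who keeps the tally can be left to the charter.

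The cost is protocol and charter wording, an extra teleconference and possibly a short enrolment pause. The fix also adds a documented route to continue where the synopsis now simply says stop. Stopping remains the default, and Section 10.9 already allows the DSMB to advise continuation.

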## **8.6 Concomitant Medication/Treatment**

Record the name, dose, start/stop date, indication for use, route, and whether ongoing or stopped for medications/treatments taken within two weeks prior to study entry as well as any medications taken during the study are to be recorded. Prohibited medications are identified in [Section 8.9](#).

## **8.7 Treatment Compliance**

Compliance will be assessed by reviewing the subject's EHR, the study medication diary when applicable, and other study records as appropriate.

## **8.8 Storage, Stability, Labeling and Packaging**

### **8.8.1 Storage and Stability**

The study drug is stored at room temperature. Stability testing is ongoing.

### **8.8.2 Labeling and Packaging**

Each brequinar bottle/dispensing container for subject use will be labeled with at least the following information:

**For Clinical Trial Use Only**

Study Number: CCB-CRISIS-01  
Contents: Brequinar 100 mg capsules  
For oral use only. Take with approximately 8 ounces water.  
Subject Number: XX-XXXX  
Treatment Duration: As directed  
Clinical Batch Number: XXXXXXXX  
Expiration Date: TBD  
Storage: Store at controlled room temperature  
Study Sponsor: Clear Creek Bio, Inc., [name],  
[name]  
Caution: New Drug – Limited by US Federal Law to Investigational Use  
Only. To be used by Qualified Investigators only.

**8.8.3 Blinding and Randomization**

The trial will be conducted in an open-label manner with random assignment to standard of care or standard of care plus brequinar. The brequinar capsules will be provided to each participating institution in bulk to be dispensed by the institution’s pharmacist for each subject. Randomization assignments will be provided by the sponsor.

**8.8.4 Unblinding/Expectedness**

It is not necessary to break the blind for this open label study as the treatment will be known for each subject.

Expectedness will be determined by establishing whether the adverse event is among those identified in the protocol and the brequinar IB or are commonly associated with COVID-19 or similar severe viral illnesses and their complications.

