### 3 INTRODUCTION

#### 3.1 Background

#### 3.2 Coronavirus-19 (COVID-19)

Beginning in December 2019, Chinese scientists isolated a novel coronavirus, severe acute respiratory syndrome coronavirus 2 (SARS-CoV-2) from patients with virus-infected pneumonia which was later designated as coronavirus disease 2019 (COVID-19) by the World Health Organisation (WHO) (Zhou et al., 2020 [2]; Phelan et al., 2020 [3]).

Approximately 14% of those affected with this virus will develop severe disease requiring hospitalization and oxygen support; 5% will require admission to the intensive care unit (Handel et al., 2020 [4]). Severe cases may be complicated by acute respiratory disease syndrome (ARDS), sepsis and septic shock, and multi-organ failure, including acute kidney injury and cardiac injury. Risk factors for death include older age and co-morbid disease such as hypertension and diabetes (Zhou, et al., 2020 [2]).

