#### **10.5 Serious Adverse Event (SAE) Reporting**

The regulatory definition of an SAE is any untoward medical occurrence or effect that at any dose:

- results in death;
- is life threatening (at the time of the event);
- requires in-patient hospitalization or prolongation of existing hospitalization;
- results in persistent or significant disability / incapacity, or
- is a congenital anomaly / birth defect;
- all other events that are considered medically serious by the Investigator.

**Disability** is defined as a substantial disruption of a person’s ability to conduct normal life functions.

**A life-threatening adverse event** is one that places the patient/subject, in the view of the Investigator, at immediate risk of death from the event as it occurred. It does not include an event that, had it occurred in a more severe form, might have caused death.

**An unexpected adverse event** is any adverse drug event, the nature or severity of which is not consistent with the applicable product information (e.g. IB for an unauthorized investigational product or summary of product characteristics for an authorized product).

PROTOCOL NUMBER: CCB-CRISIS-01  
PROTOCOL VERSION FINAL DATE: 10SEPT2020

Page 42 of 58

Enter only one event as the reason for the SAE on the SAE form. Other non-serious events which did not directly result in the SAE should be detailed in the description section on the SAE form and listed separately as AEs if necessary. For fatal SAEs, report the cause of death as an SAE with a fatal outcome rather than reporting death as the SAE term.

Note that hospitalizations for the following reasons should not be reported as SAEs:

- Routine treatment or monitoring of the studied indication, not associated with any deterioration in condition;
- Elective or pre-planned treatment for a pre-existing condition that is unrelated to the indication under study and has not worsened since signing the informed consent;
- Social reasons and respite care in the absence of any deterioration in the subject's general condition;
- Note that treatment on an emergency outpatient basis that does not result in hospital admission and involves an event not fulfilling any of the definitions of an SAE given above is not an SAE.

Death due to disease progression is considered to be an Expected event in patients with severe SARS-CoV-2 infection and does not require reporting on an expedited basis.

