## 10.6 Suspected Unexpected Serious Adverse Reactions (SUSARs)

Suspected, unexpected, serious adverse reactions (SUSARs) are SAEs that are both related to the study drug (Relationship = Related) and unexpected (not previously described in the investigator's brochure). All SUSARs will be reported in an expedited manner to the Sponsor or designee and IRB by the Investigators and to all relevant regulatory authorities by the Sponsor. Expectedness will be judged by the Medical Monitor and site Investigator. It is critical that all SAEs are reported within the 24-hour guideline so that the expectedness determination can be made. SUSARs require immediate attention and expedited reporting to relevant regulatory authorities.

The Sponsor is to ensure that all relevant information about **fatal or life-threatening** SUSARs are appropriately recorded and reported to the concerned Regulatory Authority and to the concerned IRB(s) within seven (7) calendar days of the date of first report to the Medical Monitor/Sponsor. Follow-up information is to be subsequently communicated to the relevant Regulatory Authority within an additional eight calendar days.

All other SUSARs are to be reported to the Regulatory Authority and to the IRB(s) concerned as soon as possible within a maximum of fifteen calendar days of first knowledge by the Medical Monitor/Sponsor.

The Medical Monitor/Sponsor or designee must also inform all Investigators studying the investigational medicinal product about SUSARs and ensure that all IRBs have been notified.

For reported deaths of a subject, the Investigator shall supply the Sponsor and the IRB(s) with requested additional information on an expedited basis.

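### Section 8.8.4 counts COVID-like events as expected while Sections 10.5 and 10.6 judge expectedness only against the product information, and nothing says which rule governs SUSAR reporting

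*Protocol*

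**What the plan says.** Four sections of the current protocol bear on whether an event is expected.

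- **Section 8.8.4 (Unblinding/Expectedness)** has two limbs. The first refers to documents: "Expectedness will be determined by establishing whether the adverse event is among those identified in the protocol and the brequinar IB". The second refers to the disease: "or are commonly associated with COVID-19 or similar severe viral illnesses and their complications". Either limb is enough.
- **Section 10.5 (SAE Reporting)** says that an unexpected adverse event "is any adverse drug event, the nature or severity of which is not consistent with the applicable product information", and gives the brochure as the example for an unauthorized product. The disease enters only once here: death from disease progression is declared expected in severe SARS-CoV-2 infection and exempt from expedited reporting.
- **Section 10.6 (SUSARs)** defines a SUSAR as an SAE that is "related to the study drug (Relationship = Related) and unexpected (not previously described in the investigator's brochure". It sets a 7-day limit for fatal or life-threatening SUSARs and a 15-day limit for the rest, and requires notice to all investigators and IRBs. On who decides, it says: "Expectedness will be judged by the Medical Monitor and site Investigator".
- **Section 10.4 (Classification of Severity)** allows expedited reporting of an expected event only where it departs in nature, intensity or frequency from the brochure's toxicity information.

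None of these sections refers to another on this point, and none ranks the rules.

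**The concern.** Expectedness is one of the elements that make a serious event a SUSAR. Two definitions that disagree mean that the same event can be expedited at one site and not at another, depending on which page the assessor opened. The synopsis allows up to 8 sites.

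The second limb of 8.8.4 is also wide. Section 3.2 names ARDS as a complication of severe COVID-19, together with "sepsis and septic shock, and multi-organ failure, including acute kidney injury and cardiac injury". Section 8.8.4 then extends to similar severe viral illnesses without listing any, and it carries no severity test, although severity is part of the definition in 10.5.

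What is at stake is external notice. Safety is the primary objective, and Sections 3.6.2 and 3.8 state that there is no brequinar safety information or experience in this disease. A drug reaction that looks like a COVID-19 complication is hard to recognise. Once an investigator has attributed one to the drug, its resemblance to the disease should not take it out of expedited reporting.

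**Working it through.** No figure in the protocol is in dispute, so there is nothing to recompute. The check is to run the same event through each rule.

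Take a serious event that the investigator judges definitely, probably or possibly related to brequinar, which is what Section 10.3 counts as drug-related. Assume the protocol does not itself name it as a brequinar reaction.

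| Related serious event | Under 8.8.4 | Under 10.5 and 10.6 | Same answer? |
|---|---|---|---|
| Described in the brochure, with consistent nature and severity | Expected | Expected | Yes |
| Not in the brochure, not typical of COVID-19 | Unexpected: SUSAR | Unexpected: SUSAR | Yes |
| Not in the brochure, typical of COVID-19 | Expected: not a SUSAR | Unexpected: SUSAR | **No** |

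The third row is the contradiction. Four conditions must hold together: the event is serious, it is judged related, it is not described in the brochure, and it is typical of COVID-19 or a similar illness. If any one fails, the COVID-19 clause does not change the outcome.

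Next, what depends on that row:

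1. **Affected:** the 7-day or 15-day report to the regulator and IRBs, and the SUSAR notice to the other investigators. All come from 10.6 and apply only to SUSARs.
2. **Not affected:** SAE reporting to the sponsor, which is due within 24 hours for any SAE (10.5).
3. **Not affected:** the DSMB reviews after 6 and 12 subjects complete Day 5, which cover adverse events and safety laboratory data without an expectedness filter (10.9.1).
4. **Not affected:** the study-level stopping rules, which count Grade 3 or 4 events in the brequinar arm (4 or more subjects with the same event, or 8 or more with any), and the individual rules, which use grade and, for Grade 3, relatedness (8.4).

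Finally, whether 8.8.4 does work that nothing else does. Section 10.3 already asks the investigator to separate drug causation from an underlying condition and gives COVID-19 as the example. An event put down to the disease at that step is not related and cannot be a SUSAR. The COVID-19 clause therefore changes the SUSAR outcome only for events that have already been attributed to the drug.

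**The case against.** The best defence is that 10.6 is the operative section. It carries its own brochure-based definition, contains no COVID-19 clause and does not point to 8.8.4. Section 8.8.4 sits among blinding and drug-supply text and does not mention SUSARs. A reader who works from the safety-reporting chapter would expedite the event. Section 10.4 might also bring it back, since a related event absent from the brochure arguably differs in nature from the brochure's toxicity information.

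This stands as a limit on the consequence. A reader might infer that such reactions would simply go unexpedited, and the documents do not support that: it follows only if 8.8.4 is the rule applied. But the defence does not remove the contradiction. The heading of 8.8.4 names expectedness and its text says how expectedness is to be determined, so an assessor has good reason to use it. Section 10.4 states a condition for expediting expected events but sets no time limit and names no recipient.

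Two further inferences are tempting and also fail. One is that the DSMB or the sponsor would miss the signal. Neither route depends on expectedness, and Section 13.1 separately obliges the sponsor to give prompt notice of findings that could harm patients. The other is that most serious events in this population would be affected. Nothing in the protocol supports such a share, and the brochure is not available. Section 8.2.1 lists infection among the commonly observed events and reports a drug-attributed death following acute renal failure, so sepsis or kidney examples may already be partly covered. ARDS and cardiac injury do not appear in that summary, but the brochure itself may describe them.

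**Conclusion.** The contradiction is real and stands in the current text. Section 8.8.4 on one side, and 10.5 with 10.6 on the other, classify a related serious event in opposite ways when it is absent from the brochure and typical of COVID-19, and no section says which prevails. If 8.8.4 is followed, the expedited reports and the notice to investigators could be missed for such an event.

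The size is bounded in kind: it concerns regulator, IRB and investigator notice only. It cannot be bounded in number without the brochure. This is an inconsistency in safety-reporting wording that touches no endpoint, estimate or analysis. It should be corrected because the drug is being used for the first time in this disease and the correction is cheap. The conclusion rests on the protocol text alone. A document not shown here that fixes the governing rule would reduce the practical risk but leave the protocol contradicting itself.

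**What to change.** Reconcile 8.8.4 with 10.4, 10.5 and 10.6:

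- Remove the COVID-19 clause from the expectedness definition in 8.8.4 and refer there to 10.5 and 10.6, so that the current brochure is the single reference for drug-related SAEs.
- Check that 10.4 reads consistently with that reference.
- Keep resemblance to COVID-19 where it already belongs, in the causality assessment of 10.3.
- State any anticipated disease events apart from the expectedness definition. This includes the existing exception in 10.5 for death due to disease progression, which removing the clause from 8.8.4 would otherwise leave as a disease-based expectedness statement.

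The change is to wording only and alters no dose, visit, endpoint or analysis. The running cost is possibly a few more expedited reports.
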